4 STUDY DESIGN AND ENDPOINTS

4.1 DESCRIPTION OF THE STUDY DESIGN

This is a multicenter prospective study of low-risk women who will be recruited if they are having an ultrasound at 36 weeks EGA or greater or if they are presenting to Labor and Delivery for induction of labor. As part of the study, women will have umbilical and middle cerebral artery Doppler studies and the CPR will be calculated by dividing the MCA PI by the UA/PI. Providers caring for study subjects will be blinded to this result. Pregnancy outcomes in women with CPR values less than the 10th percentile for gestational age will be compared to those with CPR values above the 10th percentile.

A secondary aim to our study is to analyze CPR as a continuous variable.

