4.2.1 PRIMARY ENDPOINT

The primary endpoint is the cesarean delivery.

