4.2.2 SECONDARY ENDPOINTS

Secondary outcomes will be obtained by chart abstraction after delivery. These include the following:

- Total cesarean section rate
- Cord blood gases
- Cases of SGA undetected prenatally.
- Birthweight/ birthweight percentile
- Incidence of category 2 or 3 tracings
- Distribution of CPR by EFW
- Rate of operative vaginal delivery
- NICU admission
- Apgar scores at 1 and 5 minute
- Composite neonatal outcome

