5.3 STRATEGIES FOR RECRUITMENT AND RETENTION

Pregnant women presenting to an obstetrical ultrasound unit or those women on labor and delivery who are not in active labor at or beyond 36 weeks EGA will be approached for enrollment in the study. Women from all ethnic backgrounds will be approached to participate. The actual percentage of minority patients will not be known until patient recruitment is completed. It is expected that there the study population will include adequate representation from a large variety of ethnic groups.

Study subjects are only being asked to undergo two additional measurements during ultrasound after they consent to the study, and we anticipate that this additional work will take no more than 5 minutes of the subject's time. Subjects will not be compensated for participating in the study.

Target sample size is for 3,000 women to enroll, which will give approximately 300 women with CPR < 10th percentile for gestational age.

Accrual rate will depend upon the number of sites participating in the research. There are currently 36,000 deliveries annually within the consortium.

No advertisements to potential study subjects are planned.

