9 STATISTICAL CONSIDERATIONS

9.1 STATISTICAL AND ANALYTICAL PLANS

Statistical analysis is expected to be straight forward in this study. Chi-square or the Fisher exact test will be used to compare binary outcomes. Continuous variables will be compared with the Student *t* test or Mann-Whitney test as appropriate.

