9.5 SAMPLE SIZE

To determine sample size we assumed a 20% cesarean rate for those women who have a CPR <10th percentile and a 10% cesarean rate in women with a CPR ≥10th percentile. With 90% power to detect a difference and $\alpha = 0.05$, 288 subjects with a CPR <10th percentile will need to be enrolled into the study. This means approximately 3,000 subjects will need to be screened.

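### With CPR groups of about 1:9, the Student t test named for continuous secondary outcomes is sensitive to unequal spread; naming the Welch t test removes this at almost no cost (minor).

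*Protocol*

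**What the plan says.** Protocol section 9.1 gives the whole analysis in a few lines. Binary outcomes go to chi-square or Fisher's exact test. For the rest, "Continuous variables will be compared with the Student *t* test or Mann-Whitney test as appropriate". It does not say how the choice between the two is made, which variance form of the t test is meant, or whether confidence intervals will be reported.

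The grouping is fixed in section 4.1: "Pregnancy outcomes in women with CPR values less than the 10th percentile for gestational age will be compared to those with CPR values above" that cut. Section 5.3 gives the resulting sizes: "Target sample size is for 3,000 women to enroll, which will give approximately 300 women with CPR < 10th percentile for gestational age". The other group is therefore about 2,700.

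The outcomes concerned are secondary. Section 4.2.2 lists "Birthweight/ birthweight percentile", cord blood gases and Apgar scores, among others. The primary endpoint is binary (section 4.2.1: "The primary endpoint is the cesarean delivery"). Section 6.2.1 adds that cord pH is recorded only where the clinical team measured it.

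**The concern.** Student's t test estimates one common variance from both groups. With groups of similar size, unequal spread does little harm to its error rate. That tolerance is lost when one group is nine times the other, and here the imbalance follows from the percentile cut, so recruiting more women does not remove it.

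The direction of the error depends on which group varies more. If the small low-CPR group is more variable, the test uses too small a standard error and finds differences too often. If it is less variable, the test is conservative and real differences are missed. Different outcomes in one results table could err in opposite directions.

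Unequal spread is plausible. The background section describes low CPR as marking some apparently well-grown fetuses with placental insufficiency, so the low-CPR group may be a mixture. The protocol does not show that the spreads differ.

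**Working it through.** **Inputs from the protocol.** 3,000 women, about 300 below the 10th percentile (section 5.3), so n₁ = 300 and n₂ = 3,000 − 300 = 2,700. Alpha is 0.05 (section 9.5); two-sided is assumed because the protocol does not say.

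**Assumed input.** r = SD in the low-CPR group ÷ SD in the other group, taken from 0.8 to 1.5. The larger group's SD is set to 1.

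**The plan's own figure.** Section 9.5 says "With 90% power to detect a difference and $\alpha = 0.05$, 288 subjects with a CPR <10th percentile will need to be enrolled". A two-sided comparison of 20% v 10% with equal groups and a continuity correction gives 286 per group, close to 288. That figure concerns the binary primary endpoint only. No sample size or SD is given for any continuous outcome.

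**Why 1:9 matters.** The low-CPR group's weight in the pooled variance is 299/2,998, about 10%. Its share of the true sampling variance at equal SDs is (1/300) ÷ (1/300 + 1/2,700) = 90%.

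**Formula.**
- True variance of the difference: V = r²/300 + 1/2,700.
- Variance the pooled test uses: P = [(299r² + 2,699)/2,998] × (1/300 + 1/2,700).
- q = √(P/V). Actual two-sided error = 2 × [1 − Φ(1.96q)].

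**Worked case, r = 1.25.** V = 1.5625/300 + 1/2,700 = 0.005579. Pooled variance = (299 × 1.5625 + 2,699)/2,998 = 1.0561, so P = 1.0561 × 0.0037037 = 0.003911. q = √(0.003911/0.005579) = 0.837. Error = 2 × [1 − Φ(1.641)] = 10.1%.

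| r (assumed) | q | Pooled t, error by formula |
|---|---|---|
| 0.8 | 1.194 | 1.9% |
| 0.9 | 1.088 | 3.3% |
| 1.0 | 1.000 | 5.0% |
| 1.1 | 0.927 | 6.9% |
| 1.25 | 0.837 | 10.1% |
| 1.5 | 0.728 | 15.4% |

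Simulation with normal data (20,000 runs per ratio) agrees: 2.0% at 0.8, 10.4% at 1.25 and 15.0% at 1.5. Groups of 150 v 1,350 give the same results, so the ratio drives the error rather than the total.

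**Cost in power when r < 1.** For a difference that a test with the correct standard error detects with 80% power, the pooled test has power Φ(1.96 + 0.842 − 1.96q). That is about 68% at r = 0.8 and 75% at r = 0.9.

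**Welch.** In the same simulations its error stays between 4.8% and 5.3% for every ratio from 0.67 to 2.0. At r = 1 it gives 5.0% against 5.1% for Student.

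**Mann-Whitney.** Simulated error (1,500 runs, Monte Carlo standard error about 0.6 points at 5% and 0.8 points at 11%) is about 3% at r = 0.8, 8% at 1.25 and 11% at 1.5, for two normal distributions with equal means. It is less affected than the pooled t test at these ratios, but not immune.

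**What ratio might occur.** The only handle in the protocol is section 9.5: "we assumed a 20% cesarean rate for those women who have a CPR <10th percentile and a 10% cesarean rate in women with" CPR at or above the cut. Suppose, purely as an illustration, that 20% and 10% are the shares of affected fetuses, and that their outcomes are shifted by δ SDs. The variances are 1 + 0.16δ² and 1 + 0.09δ². For δ = 2, 3 and 4 the SD ratios are √(1.64/1.36) = 1.10, √(2.44/1.81) = 1.16 and √(3.56/2.44) = 1.21. A pooled 95% interval, if reported, would then cover about 93%, 92% and 91%.

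**The case against.** **The wording does not commit to the pooled test.** The sentence also offers Mann-Whitney, leaves the choice open and never mentions equal variances. Student's t is sometimes loose shorthand for any two-sample t test. This stands in part: Welch is not excluded. But the name ordinarily means the pooled form, and an analyst following 9.1 literally would run it. The Mann-Whitney option does not protect the outcomes that are compared by means.

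**It is detail for a statistical analysis plan.** Had 9.1 been silent on the test, this would settle the matter. It names one, and a better one is available by changing a word.

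**The harm is undocumented.** This stands. The protocol gives no SDs, and at ratios of 0.9 to 1.1 the error is only 3% to 7%. The mixture illustration reaches about 1.2 even with large shifts. It also treats cesarean rates as rates of fetal compromise, which they are not. In that illustration the means differ by 0.1δ, so the null is false; it speaks to interval coverage, not to false positives.

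A reader might infer more than the documents support:
- That the p values and confidence intervals for birthweight and cord pH are wrong. Nothing shows that the spreads differ, and no intervals are planned.
- That 300 v 2,700 applies to every outcome. Cord pH is recorded only where it was done, so its numbers will be smaller and its ratio is unknown.
- That Mann-Whitney must also be replaced. It is valid for its own null of identical distributions, which is a legitimate reading of no association with CPR. A substitute such as the Brunner-Munzel test is a preference.

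**Conclusion.** The point holds as a minor improvement. Section 9.1 names a test whose usual form tolerates unequal spread poorly at about 1:9. The nominal 5% error rate would be about 2% to 15% over assumed SD ratios of 0.8 to 1.5, and 3% to 7% over 0.9 to 1.1. This rests on three assumptions: that Student means the pooled form, that the projected share of about 10% below the cut is realised among women with data, and that the test is two-sided. The size of any actual harm cannot be read from the protocol and is probably modest. The primary endpoint, its test and the sample size are unaffected, and no main conclusion of the study depends on this.

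**What to change.** In section 9.1, replace the Student t test by the Welch (unequal-variance) t test wherever means are compared. Mann-Whitney may stay for ordinal or skewed outcomes such as Apgar scores. The cost is a change of words, with no extra data or participants. When the SDs are equal, the Welch test behaves almost exactly like Student's at these group sizes. The change is best made before outcomes are analysed, so that the choice of test cannot depend on the results.

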9.5 SAMPLE SIZE

To determine sample size we assumed a 20% cesarean rate for those women who have a CPR <10th percentile and a 10% cesarean rate in women with a CPR ≥10th percentile. With 90% power to detect a difference and $\alpha = 0.05$, 288 subjects with a CPR <10th percentile will need to be enrolled into the study. This means approximately 3,000 subjects will need to be screened.

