6.3.2 ENROLLMENT/BASELINE

When the study subject has her ultrasound, the fetus must not be growth restricted as defined by a composite EFW of less than the 10th percentile to continue participation in the study.

The ultrasound assessment of Doppler studies must be complete. If the sonographer cannot obtain satisfactory measurements of both vessels, this information will be recorded but additional subjects will need to be recruited to meet sample size requirements.

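### The 288 low-CPR women in section 9.5 fit an equal-group comparison, not the roughly 1:9 comparison planned, so the stated 90% power understates the design's power under its own assumptions

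*Protocol*

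**What the plan says.** Protocol section 9.5 states its assumption for the low-CPR group, "we assumed a 20% cesarean rate for those women who have a CPR <10th percentile". For the comparison group it takes "a 10% cesarean rate in women with a CPR ≥10th percentile". The power is introduced by "With 90% power to detect a difference", alpha is 0.05, and the requirement reads: "288 subjects with a CPR <10th percentile will need to be enrolled into the study". It then says that "approximately 3,000 subjects will need to be screened". It does not state the allocation ratio, the size of the comparison group, whether the test is one- or two-sided, or the formula.

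Section 4.1 defines the comparison: "women with CPR values less than the 10th percentile for gestational age will be compared to those with CPR values above the 10th percentile". No sampling of the larger group is described. Section 5.3 says: "Target sample size is for 3,000 women to enroll, which will give approximately 300 women with CPR < 10th percentile for gestational age". Section 9.1 names the chi-square or Fisher exact test for binary outcomes. Section 6.3.2 says that when Dopplers are unsatisfactory, "additional subjects will need to be recruited to meet sample size requirements".

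The primary endpoint is given in two ways. The summary table at the front names cesarean for non-reassuring fetal heart tracings; section 4.2.1 names cesarean delivery without qualification. The rates in section 9.5 are likewise unqualified.

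**The concern.** A cutoff at the 10th percentile splits one cohort into groups of about 300 and 2,700. A sample size for that comparison has to use that ratio, because a large comparison group contributes precision that two equal groups would not. If 288 was computed for equal groups, the stated power belongs to a design that is not being run. The smallest difference the study can reliably detect is then also misdescribed. In an observational study asking whether CPR predicts outcome, that detectable difference is one of the main things a reader takes from the sample-size section.

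**Working it through.** **Inputs.** p1 = 0.20, p2 = 0.10, power 0.90 and alpha 0.05 (section 9.5). Ratio r = 2,700/300 = 9 (sections 4.1 and 5.3). Two-sided testing is assumed because the protocol does not say; one-sided was also tried.

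**Formula** (pooled variance, smaller group n1, d = p1 − p2, p̄ = (p1 + r·p2)/(1 + r)):

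n1 = [1.960·√((1 + 1/r)·p̄(1 − p̄)) + 1.2816·√(p1(1 − p1) + p2(1 − p2)/r)]² / d²

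With continuity correction: n1′ = (n1/4)·[1 + √(1 + 2(r + 1)/(r·n1·d))]²

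**Step 1: the plan's own figure, equal groups (r = 1).** p̄ = 0.15.
- n1 = [1.960·√0.255 + 1.2816·√0.25]² / 0.01 = (0.9898 + 0.6408)² / 0.01 = 265.9, so 266 per group.
- Corrected: (265.9/4)·[1 + √1.1505]² = 285.5, so 286 per group.
- Other equal-group versions: unpooled 263, arcsine 261, one-sided 217 (237 corrected).
- Power at 288 v 288 is 92.1% by the uncorrected formula and about 91% for Fisher's exact test by simulation.

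The corrected two-sided figure of 286 is the nearest to 288, though not identical.

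**Step 2: the planned comparison (r = 9).** p̄ = 0.11.
- n1 = [1.960·√0.10878 + 1.2816·√0.17]² / 0.01 = (0.6464 + 0.5284)² / 0.01 = 138.0 (138.02 before rounding), so 139 low-CPR women, 1,390 in total.
- Corrected: (138.0/4)·[1 + √1.1610]² = 148.9, so 149 low-CPR women, 1,490 in total.
- Other 1:9 versions: arcsine 145, unpooled 179, one-sided 115 (126 corrected). None comes near 288.

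**Step 3: power for 20% v 10% with the planned numbers.** z = (d·√n1 − 0.6464)/√0.17.
- 288 v 2,592: (1.6971 − 0.6464)/0.4123 = 2.548, power 99.5%. A Fisher exact simulation gives about 99%.
- 300 v 2,700: (1.7321 − 0.6464)/0.4123 = 2.633, power 99.6%.

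**Step 4: detectable difference at 300 v 2,700.** For 16.5% v 10%, p̄ = 0.1065 and z = (0.065·√300 − 1.960·√0.10573)/√0.14778 = (1.1258 − 0.6373)/0.3844 = 1.271, power 89.8%. So 90% power is reached at about 16.5% v 10%, a difference of 6.5 points rather than 10.

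**Step 5: dependence on the endpoint.** The protocol gives no rate for cesarean for non-reassuring tracings. As an illustration only, with assumed comparison-group rates doubled in low-CPR women and 300 v 2,700:

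| Assumed rates | Power |
|---|---|
| 4% v 2% | 59% |
| 6% v 3% | 73% |
| 8% v 4% | 83% |
| 10% v 5% | 90% |

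**Step 6: the 3,000.** 288/0.10 = 2,880, which rounds to about 3,000. Ten percent of 3,000 is 300, and (300 − 288)/300 = 4%, so 3,000 measured women cover 288 with a 4% margin.

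**The case against.** The best defense is that nothing is lost. Under the stated assumptions the plan delivers more than the 90% it promises. No test, estimate, type I error rate or population changes, and participation is one visit with about five extra minutes. All of that stands. It limits the importance of the point but does not make the stated requirement the right one for the design.

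It is also fair to say that equal groups and a continuity correction are inferred. Section 9.5 states no method, and 286 is not 288. The inference concerns only where 288 came from. That 288 is about twice what the 1:9 comparison needs does not depend on it.

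A reader might go further in three ways that the documents do not support.

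- **That the surplus allows a cut to about 150 low-CPR women.** This holds only for cesarean for any indication. If the summary table's endpoint governs, Step 5 shows that even 300 v 2,700 could fall short of 90%.
- **That 'enroll' in section 5.3 and 'screened' in section 9.5 set two different stopping points.** Section 6.3.1 does use screening for the approach before consent, so the wording is loose. But in section 9.5 the word follows directly on 288 low-CPR women and can be read as the number whose CPR must be measured, which agrees with section 5.3. Section 6.3.2 also provides for replacing unsatisfactory Dopplers.
- **That a null result would be misjudged.** The protocol has no rule that interprets a null result by planned power, and a null result from a study with more power than stated is more informative, not less.

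**Conclusion.** The point holds, as an error on the safe side. For 20% v 10% at two-sided 0.05, section 9.5 asks for about twice the low-CPR women that 90% power requires (288 against 139 to 149). It reports as 90% a power that is about 99.5% with the planned numbers. The difference detectable with 90% power is about 6.5 points above a 10% rate.

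This rests on a 1:9 split, two-sided testing, women with complete data, and cesarean for any indication as the outcome. The last assumption is the fragile one, since the protocol names two primary endpoints.

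This should be fixed, but it does not threaten the study: for cesarean for any indication the sample is more than adequate. The enroll/screened difference is a minor matter of wording.

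**What to change.** - Restate section 9.5 for the comparison actually planned: about 300 v 2,700, the ratio, the sidedness, the method, and either the power for 20% v 10% (over 99%) or the difference detectable with 90% power (about 16.5% v 10%). Keep 3,000.
- State in section 9.5 that these figures apply to cesarean for any indication. Reconcile the summary table with section 4.2.1, and if the primary endpoint is cesarean for non-reassuring tracings, recompute with rates for that outcome. Do not consider a smaller sample before this is settled.
- Use one term for the 3,000 in sections 5.3 and 9.5, such as women with complete Dopplers.

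The cost is protocol wording and, if the narrower endpoint is chosen, one new calculation. No additional patients are needed for the comparison as section 9.5 now states it.

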9.6 MEASURES TO MINIMIZE BIAS

9.6.1 ENROLLMENT/ RANDOMIZATION/ MASKING PROCEDURES

Not applicable.

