	pregnancies complicated by IUGR. The CPR may predict adverse outcomes in low risk pregnancies. In a prospective study, we will examine whether fetuses with an abnormal CPR at or near term are at increased risk for being delivered by cesarean
Objective	To assess whether women with appropriately grown fetuses in otherwise low risk pregnancies with an abnormal CPR are more likely to be delivered by cesarean section
Endpoints	
Primary outcome variable:	Cesarean for non-reassuring fetal heart tracings
Secondary outcome variables:	Total cesarean delivery rate Umbilical cord blood pH Unidentified small for gestational age births Birthweight percentile Prevalence of category 2 or 3 fetal heart tracings Distribution of CPR by EFW Rate of operative vaginal delivery NICU admission Apgar scores at 1 and 5 minutes Composite neonatal outcome
Population	Healthy women with low-risk pregnancies receiving care at study institutions
Number of Sites enrolling participants	8
Description of Study Agent	Prenatal ultrasound Doppler assessment of the umbilical and middle cerebral arteries
Study Duration	12 months
Participant Duration	Between 1 day and 6 weeks

SCHEMATIC OF STUDY DESIGN

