6 STUDY PROCEDURES AND SCHEDULE

6.1 STUDY PROCEDURES/EVALUATIONS

6.1.1 STUDY SPECIFIC PROCEDURES

- Study personnel will identify subjects who meet inclusion criteria and none of the exclusion criteria and approach them for informed consent to participate in the study.
- Once a subject agrees to participate, a brief obstetrical history will be obtained.
- If subjects' clinically indicated ultrasound study is normal, Doppler measurements of the umbilical and middle cerebral arteries will be obtained three times each and the mean value of the PI will be used to determine the CPR. Data will be recorded on study forms.
- The subject's medical record will be abstracted to obtain relevant data on study forms. Mode of delivery, whether this was a diagnosis of fetal compromise and managing physician's diagnoses will be obtained from the maternal chart. Birthweight, 1 and 5 minute Apgars scores, cord blood gasses (if done) and NICU admission will be recorded. The newborn birth record will also be reviewed for specific complications including need for supplemental oxygen, intracranial hemorrhage, hypoglycemia, jaundice, an unspecified complications.

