6.1.2 STANDARD OF CARE STUDY PROCEDURES

Standard of care will not be impacted by a subjects' enrollment in the study. The only difference in care will be assessment of the middle cerebral and umbilical artery by Doppler in women who consent to participate in the study. Clinical care providers will be blinded to the Doppler results. There will be no involvement of study personnel on Labor and Delivery. All data recorded for maternal and neonatal outcomes will be obtained by chart abstraction after delivery has occurred.

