6.3.7 SCHEDULE OF EVENTS TABLE

Procedures	Enrollment (Only Subject Visit)	Delivery Chart Abstraction	
Informed Consent	X		
Demographics	X		
Medical History			
Height			
Weight	X		
Middle Cerebral Artery Doppler	X		
Umbilical Artery Doppler	X		
CPR Calculation	X		
Maternal data		x	
Neonatal data		x	

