11 QUALITY ASSURANCE AND QUALITY CONTROL

Central Webinar trainings will be conducted for consistency and quality control. Sites will not enroll patients until the research staff and sonographer training is complete. There will be a random review of data from every site for quality assurance.

Paper data collection forms, de-identified and coded, will be completed at each site and sent to Rutgers- Robert Wood Johnson Medical School, the Data Coordinating Center (DCC). The data will be entered centrally at the DCC for quality control purposes. The sites will be responsible for data queries and assisting the DCC with data discrepancies for quality assurance.

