13 DATA HANDLING AND RECORD KEEPING

13.1 DATA COLLECTION AND MANAGEMENT RESPONSIBILITIES

Data collection is the responsibility of the clinical trial staff at the site under the supervision of the site PI. The investigator is responsible for ensuring the accuracy, completeness, legibility, and timeliness of the data reported.

All source documents should be completed in a neat, legible manner to ensure accurate interpretation of data. Black ink is required to ensure clarity of reproduced copies. When making changes or corrections, cross out the original entry with a single line, and initial and date the change. **DO NOT ERASE, OVERWRITE, OR USE CORRECTION FLUID OR TAPE ON THE ORIGINAL.**

Copies of the CRF will be provided for use as source documents and maintained for recording data for each participant enrolled in the study. Data reported in the CRF derived from source documents should be consistent with the source documents or the discrepancies should be explained and captured in a progress note and maintained in the participant's official electronic study record.

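### Section 9.6.1 marks masking as not applicable, and nothing in the protocol keeps the staff who abstract outcomes from charts unaware of the CPR

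*Protocol*

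**What the plan says.** **Masking.** Section 9.6.1, "ENROLLMENT/ RANDOMIZATION/ MASKING PROCEDURES", stands under the heading on measures to minimize bias and is answered only with not applicable. So are 9.6.2 and 9.6.3. Yet 6.1.2 states that "Clinical care providers will be blinded to the Doppler results". Sections 2.3.1 and 4.1 say the same, and 2.3.1 adds an exception at the principal investigator's discretion.

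**Exposure.** The schedule in 6.3.7 places "CPR Calculation" at the enrollment visit. Under 6.1.1 the Doppler data go on study forms.

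**Outcome.** Section 6.1.1 has the chart abstracted for "Mode of delivery, whether this was a diagnosis of fetal compromise", the managing physician's diagnoses and newborn complications. By 6.1.2 this happens after delivery.

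**Who does it.** Section 13.1: "Data collection is the responsibility of the clinical trial staff at the site". By section 11 the paper forms are completed at each site, and "The data will be entered centrally at the DCC for quality control purposes".

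**Primary outcome.** The synopsis names "Cesarean for non-reassuring fetal heart tracings". Section 4.2.1 states: "The primary endpoint is the cesarean delivery". Both the synopsis and 4.2.2 list total cesarean as secondary.

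**The concern.** Blinding the providers protects the decision to operate. It does not protect the later step in which someone reads the chart and records why the operation was done. Charts with more than one indication, such as slow progress together with an abnormal tracing, leave room for judgement. If the abstractor knows the CPR was low, such cases may be assigned to the fetal indication more often in that group than in the other.

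That would be differential misclassification in the direction of the hypothesis. Covariate adjustment cannot remove it, and a larger sample makes a false positive more likely, because the bias stays while the standard error shrinks. A later analysis plan cannot repair it either: once the charts have been abstracted with the CPR known, masking cannot be restored.

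**Working it through.** **1. The protocol's own figure.** Section 9.5 assumes 20% v 10% cesarean, 90% power and alpha 0.05, and states 288 women with CPR below the 10th percentile. A two-sided, 1:1, continuity-corrected calculation gives 286, so the figure reproduces closely. It refers to any cesarean, and masking does not change it. Section 5.3 expects about 300 such women among 3,000, hence 300 v 2,700 below.

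**2. Path from exposure to outcome.**
- CPR known: from the enrollment visit (6.3.7).
- Forms completed: at the site (11), by site trial staff (13.1).
- Outcome recorded: by chart abstraction after delivery (6.1.1, 6.1.2, 6.3.3).
- Persons blinded: care providers only (2.3.1, 4.1, 6.1.2).
- Check on coding: remote data review, not described as masked to CPR, and no independent audits (8, 11).

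No section blinds the abstractor, separates the roles or forms, or adjudicates the indication.

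**3. Illustration A, no true effect.** All coding inputs are assumptions. Coded rate = clear fetal indication + P(mixed coded as fetal) × mixed.
- Mixed 3%, coded fetal 60% v 40%: 0.04 + 0.6 × 0.03 = 0.058 v 0.04 + 0.4 × 0.03 = 0.052; risk ratio 1.12.
- Mixed 4%, coded fetal 70% v 40%: 0.04 + 0.7 × 0.04 = 0.068 v 0.04 + 0.4 × 0.04 = 0.056; risk ratio 1.21.

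False-positive rate of the two-sided pooled z test: Φ((d − 1.96·s0)/s1) + Φ((−d − 1.96·s0)/s1), where d is the difference, s0 the pooled and s1 the unpooled standard error. First case: pooled rate (300 × 0.058 + 2,700 × 0.052)/3,000 = 0.0526, s0 = 0.01359, s1 = 0.01416, d = 0.006. This gives Φ(−1.457) + Φ(−2.305) = 0.073 + 0.011 = 8.3%. The second case gives 15.5%.

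**4. Illustration B, no true effect.** Total cesarean T is equal in both groups, and a share s is truly for non-reassuring tracings. A fraction f of the other cesareans is recoded to that indication in the low-CPR group only. Then p2 = T·s and p1 = p2 + f·(T − p2).

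| T | s | f = 10%: p1 v p2, RR, false positive | f = 20%: p1 v p2, RR, false positive |
|---|---|---|---|
| 10% | 30% | 3.7% v 3.0%, 1.23, 12.4% | 4.4% v 3.0%, 1.47, 29.2% |
| 10% | 50% | 5.5% v 5.0%, 1.10, 7.5% | 6.0% v 5.0%, 1.20, 13.4% |
| 20% | 30% | 7.4% v 6.0%, 1.23, 18.0% | 8.8% v 6.0%, 1.47, 47.8% |
| 20% | 50% | 11.0% v 10.0%, 1.10, 9.3% | 12.0% v 10.0%, 1.20, 20.8% |

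**5. Any cesarean.** Moving a case between indications leaves T unchanged, so the comparison of total cesarean is not affected.

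**The case against.** - **The entry covers enrollment, randomization and masking together, in an observational study.** Not applicable is a natural answer for randomization. It is still inaccurate for masking, which the protocol uses elsewhere.
- **The charted diagnosis comes from blinded providers.** This stands and is the main limit on the concern. Apart from the exception in 2.3.1, the risk is confined to charts that need interpretation, and the protocol does not say how common these are.
- **A reader might infer that the same staff calculate the CPR and code the outcome.** The protocol does not say so. It does not say who calculates the CPR, whether Doppler and delivery data share a form, or where the percentile group is assigned. Sonographers are a distinct role, and 13.3 refers to a MOP that is not shown. What can be said is that nothing in the protocol prevents the overlap.
- **A reader might infer that the primary outcome is affected in any case.** That holds only under the synopsis. Under 4.2.1, and with the cesarean rates in 9.5, the primary is any cesarean and indication coding does not touch it. Listing total cesarean as secondary favors the synopsis reading but does not settle it.
- **The shift is small against the planned effect.** Illustration A moves the difference by 0.6 to 1.2 percentage points, or 300 × 0.006 = 1.8 to 300 × 0.012 = 3.6 women, against 10 points planned for any cesarean. It could not by itself produce an effect of that size. It can still raise the false-positive rate for the indication-specific outcome.

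**Conclusion.** The concern holds as a preventable gap, not as a demonstrated bias. Section 9.6.1 conflicts with the provider blinding stated elsewhere, and no rule keeps abstractors unaware of the CPR. Cesarean for non-reassuring tracings, tracing category and neonatal complications may be coded with the exposure known; total cesarean is unaffected.

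The size is unknown. The false-positive rates of 8.3% and 15.5%, and the wider 7.5% to 47.8% in the table, rest on assumed indication shares and coding behavior and show only what is possible. Whether the primary outcome is at risk depends on how the synopsis and 4.2.1 are reconciled.

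**What to change.** Replace the entry in 9.6.1 with:
1. The provider blinding already stated in 2.3.1, 4.1 and 6.1.2.
2. Doppler and CPR data go on a form separate from the delivery and neonatal forms.
3. Delivery and neonatal outcomes are abstracted without access to that form or to the CPR group.
4. The DCC assigns the percentile group and links it to outcomes only after the outcome form is locked.
5. Each use of the exception in 2.3.1 is logged.

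The Doppler form need not reach the DCC before delivery. That would often be impossible, because women may be recruited at induction (4.1) and participation can last one day (synopsis). The CPR may still be calculated at the site by someone other than the abstractor, so the exception in 2.3.1 can operate.

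Separately, reconcile the synopsis and 4.2.1 on the primary outcome.

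The cost is some form handling and role separation at the sites, which may be a burden where research staff are few. Central entry at the DCC already exists.
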